7.2.8. Subgroup Analyses

Subgroup analyses of the dysmenorrhea and NMPP responder analyses at Week 104/EOT will be performed to assess whether responder rate is consistent across clinically important subgroups. The responder rate and 95% CI may be displayed for each subgroup. Subgroups will include, but will not be limited to, the subgroups outlined in Table 16.

Table 16: Planned Subgroup Analyses

Subgroup Name	Subgroup Level
Geographic region	North America, Rest of World
Age (years)	< 35, ≥ 35; < 30, 30 to < 35, 35 to < 40, ≥ 40
Race	Black or African American, White
BMI (kg/m ²) at Baseline	< 30, ≥ 30; < 18.5, 18.5 to < 25, 25 to < 30, 30 to < 35, 35 to < 40, ≥ 40; <25, 25 to < 30, ≥30

Abbreviations: BMI = body mass index;

7.3. Secondary Efficacy Endpoints

All secondary efficacy measures over the course of both the pivotal phase 3 and extension studies will be presented by the pivotal phase 3 study treatment group using descriptive statistics. No treatment comparisons will be performed for this extension study.

7.3.1. Change from Baseline in EHP-30 Pain Domain Scores

No imputations will be made for missing values in the EHP-30 Pain Domain scores.

The score for an EHP-30 domain is calculated by adding the scores for individual items (each with five response options scored from 0 to 4) to obtain a total raw score, then dividing by the highest possible raw score and multiplying the result by 100 to obtain a normalized score that ranges from 0 to 100. For each domain, the normalized score is:

$$\text{Normalized score} = (\text{Total raw score} / \text{Total raw score range}) \times 100$$

The normalized score is used for analysis. Higher scores represent a greater (ie, more negative) functional impact of endometriosis. The domains are provided in Table 17.

The mean change and percent change from pivotal phase 3 study baseline by visit of pivotal phase 3 study and extension study will be analyzed for pain domain and each of the non-pain domains (Control and Powerlessness, Social Support, Emotional Well-Being, and Self-Image). LS means and 95% CI are based on mixed-effects model with visit, treatment, treatment-by-visit interaction, region (North America, Rest of World), time since initial surgical diagnosis of endometriosis (< 5, ≥5 years), and baseline value included as fixed effects. The multiple visits for each patient are the repeated measures as random effects within each patient, and an unstructured covariance matrix is assumed. If the mixed-effects model fails to converge, a first-

order autoregressive variance-covariance matrix will be used. Here treatment refers to pivotal phase 3 study treatment group.

In addition, proportion of patients who are responders of EHP-30 pain domain will be determined and summarized by pivotal phase 3 study treatment group. The prespecified clinically meaningful threshold of ≥ 20 points decrease from baseline will be used.

Responder rate and two-sided 95% CI based on Clopper-Pearson exact binomial will be presented for Week 52 and Week 104. For each question of the EHP-30 Pain Domain, the proportion of patients in each category at Week 52 and Week 104 will be described. The percentage of patients shifting from Baseline “often/always” to post-baseline “never/rarely” will also be summarized for each question at Week 52 and Week 104.

Table 17: Endometriosis Health Profile 30-Item Questionnaires Scores

Domain	Items	Lowest and Highest Possible Total Raw Scores	Total Raw Score Range
Pain	1 – 11	0, 44	44
Control and Powerlessness	12 – 17	0, 24	24
Emotional Well-Being	18 – 23	0, 24	24
Social Support	24 – 27	0, 16	16
Self-Image	28 – 30	0, 12	12

7.3.2. Change from Baseline in Numerical Rating Scale Score for Endometriosis-Associated Pain

Patients assessed endometriosis-associated pain using an NRS as part of their daily eDiary entries. Patients rated their worst pelvic pain in the past 24 hours on a scale from 0 to 10, with 0 indicating no pain and 10 indicating pain as bad as you can imagine. Patients also recorded whether they had menstruated in the past 24 hours. The mean NRS score for DYS during the Week 52, Week 104/EOT pain assessment period is calculated as the average of the pain scores recorded on days for which patients reported they were menstruating. The mean NRS score for NMPP during the Week 52, Week 104/EOT pain assessment period is calculated as the average of the pain scores recorded on days on which patients reported they were not menstruating. The mean NRS scores for DYS and NMPP are calculated in a similar manner during the pivotal phase 3 studies baseline pain assessment period.

The mean NRS score of overall pelvic pain for Week 52 and Week 104/EOT pain assessment periods will be based on all pain scores recorded without regard for menstruation status. The mean NRS score of dyspareunia for Week 52 and Week 104/EOT pain assessment periods will be based on the pain scores recorded on days when the patient reported having vaginal sexual intercourse. This analysis will be performed in the subgroup of patients with baseline dyspareunia defined as having a non-zero baseline dyspareunia score.

The mean change and percent change of NRS score from baseline to Week 52, and to Week 104/EOT will be presented by the pivotal phase 3 study treatment group for DYS, NMPP, overall pelvic pain, and dyspareunia separately. LS means and 95% CI are based on mixed-effects model with visit, treatment, treatment-by-visit interaction, region (North America, Rest of World), time since initial surgical diagnosis of endometriosis (< 5 , ≥ 5 years), and baseline

value as fixed effects; The multiple visits for each patient are the repeated measures as random effects within each patient, and an unstructured covariance matrix is assumed. Here treatment refers to pivotal phase 3 study treatment group.

The number and percentage of patients with following NRS categories will be presented by visit and by the pivotal phase 3 study treatment group for DYS, NMPP separately.

- < 4 vs \geq 4
- < 4, 4 - < 7, 7 - 10

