4. GENERAL CONSIDERATIONS FOR DATA ANALYSES AND HANDLING OF MISSING DATA

4.1. Data Presentation Conventions

All statistical analyses will be conducted using SAS[®] Version 9.2 or higher. Only descriptive analyses will be provided. Formal statistical comparisons are not planned.

All confidence intervals (Cis) will be reported as two-sided 95% Cis unless otherwise stated.

Where appropriate, variables will be summarized descriptively by study visit. For the categorical variables, the count and proportions of each possible value will be tabulated by pivotal phase 3 study treatment group. For continuous variables, the number of patients with non-missing values, mean, median, standard deviation (SD), minimum, and maximum values will be tabulated.

Unless otherwise specified, the following conventions will be applied to all analyses:

- Mean and median values will be formatted to one decimal place, unless otherwise specified. For BMD DXA, mean and median values will be formatted to two decimal places. Standard deviation values will be formatted to two more decimal places, unless otherwise specified. Minimum and maximum values will be presented to the same number of decimal places as the measured value. If the measured value is large (eg, > 100), fewer decimal places may be displayed.
- Percentages will be rounded to one decimal place.
- P values will be rounded to four decimal places. P values < 0.0001 will be presented as "< 0.0001" and p values > 0.9999 will be presented as "> 0.9999".
- 1 month = 30.4375 days. Month is calculated as (days/30.4375) rounded to one decimal place.
- 1 year = 365.25 days. Year is calculated as (days/365.25) rounded to one decimal place.
- Age will be calculated using the date of randomization in pivotal phase 3 study. If only year of birth is collected, 1 July of the year of birth will be used to calculate age.
- 1 pound = 0.454 kg.
- 1 inch = 2.54 cm.
- Missing efficacy or safety data will not be imputed, unless otherwise specified.
- For laboratory results above or below sensitivity limits displayed as "<" or ">" a quantification threshold, 0.000000001 will be subtracted or added, respectively, to the threshold to derive a numeric result for analysis.
- For safety analyses, percentages will be calculated based on the number of patients in the analysis population in each pivotal phase 3 study treatment group.

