4.4.1. By-Visit Endpoints

By-visit endpoints will be analyzed using observed data, unless otherwise specified. For observed data analyses, missing data will not be imputed and only the observed records will be included.

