7.1.2. Analyses for Continuous Data

Continuous variables will be summarized using descriptive statistics (eg, n, mean, median, SD, minimum, and maximum). For the analyses of change from Baseline, the mean at Baseline will be calculated for all patients with at least one post-Baseline value by pivotal phase 3 study treatment group. Additionally, the mean will also be calculated for each visit, including only the patients who are in the analysis who have data for that visit by pivotal phase 3 study treatment group.

For endpoints evaluating the change (absolute or percent change) from Baseline to Week 52 or Week 104/EOT, mean change as well as least squares (LS) means change and 95% CI will be summarized. LS means and 95% CI will be derived using a mixed-effects model repeated

measures approach with pivotal Phase 3 study randomization stratification factors, visit, treatment, and treatment-by-visit interaction included as fixed effects. Here treatment refers to pivotal Phase 3 study treatment group. The Baseline value will be included as a covariate, and an unstructured variance-covariance matrix will be assumed. If the mixed-effects model fails to converge, a first-order autoregressive variance-covariance matrix will be used. Calculation of the dependent variable (change from Baseline) for each patient at each visit will be calculated based on the visit windows specified in Section 4.3.8. In addition, summary statistics (mean change or mean % change) will be graphically presented as appropriate.

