35 calendar days immediately prior to and including the date of last dose of study drug;

- If the date of last dose occurs outside of the eDiary collection period or there are not 35 calendar days prior to the last dose of extension study drug from the eDiary collection period that includes the last dose, the PAP will be the last 35 days in the eDiary collection day on or prior to the last dose of study drug, from the last one or two eDiary collection periods.
- If the last 35 calendar days prior to and including date of last dose of study drug are not entirely within an eDiary collection period:
 - if the date of last dose occurs during the eDiary collection period, the PAP will be the last 35 days which are counted during up to two eDiary collection periods immediately prior to and including date of last dose of study drug
 - if the date of last dose occurs outside of the eDiary collection period, the PAP will be the last 35 days which are counted during up to two eDiary collection period(s) immediately prior to but not including date of last dose of study drug

Week 104/EOT analgesic use for pelvic pain is the average daily pill count as reported in the eDiary during the Week 104/EOT PAP. The average daily pill count will be calculated separately for Tier 1 and Tier 2 analgesics for Week 104/EOT.

NRS pain scores and analgesic use during PAP of each of other study weeks will be calculated for efficacy analysis by visit. Pain scores for DYS and NMPP are the averages of the respective eDiary pain scores reported during each individual PAP. Analgesic use for pelvic pain is the average daily pill count as reported in the eDiary during each individual PAP.

For Week 65, 78, 91 and 104, PAP is defined as the total days of ed diary collection period immediately prior to respective week. For Week 28 to Week 48, PAP is defined as the last 35 calendar days of extension study treatment immediately prior to respective week. For patients with extension study treatment duration less than 35 days, PAP is defined as the days between the first dose of extension study drug and date of last dose of extension study drug. **Definition of Increased Use of Analgesics**

The definition of increased analgesic use in pivotal phase 3 studies will be applied to this extension study. Protocol-specified analgesic medications for endometriosis-associated pain will be analyzed based on the following categories:

- Tier 1
 - Ibuprofen (200 mg)
- Tier 2:

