7.2.6. Derivation of Responder Status at Week 52, Week 104/EOT and Missing Data Handling Rules

For the primary efficacy analysis, both primary endpoints will incorporate the missing data handling rules at Week 52, Week 104/EOT as follows (Table 14, Table 15 and Figure 2):

- For patients missing eDiary for all visits in the extension study, their Baseline/Week 24 responder status from the pivotal phase 3 study will be carried over as their responder status to Week 52, Week 104/EOT.
- For patients who have any pain score entries in eDiary in the extension study, responder status for DYS and NMPP will be derived as follows:
 - For DYS, the responder status will be defined using the following rules taking analgesic use into consideration (Table 14):
 - If there are at least 2 days of DYS NRS scores reported in the eDiary, then the average will be calculated and used in the assessment of the DYS responder status. Requiring a minimum of 2 days of DYS NRS scores is considered reasonable since a typical menstrual cycle has bleeding days ranging from 3 to 7 days.
 - If there are < 2 days of NRS scores for DYS reported in the eDiary, then the following scenarios will be considered:
 - If no DYS scores are reported in the eDiary, then the data collected on the menstruation eCRF will be considered as follows:
 - If no menstruation is reported on the eCRF, then the average DYS score will be set as 0;
 - Otherwise, if any menstruation days are reported on the eCRF, then the average DYS score will be set as missing and will be imputed using a mixed-effects model.

- If only one DYS score is reported in the eDiary, then the data collected on the menstruation eCRF will be considered as follows:
 - If no more than one menstruation day is reported on the eCRF, then the observed DYS score will be taken as the average DYS score;
 - If more than one menstruation day is reported on the eCRF, then the average DYS score will be considered missing and will be imputed using a mixed-effects model.
- For NMPP, the responder status will be defined using the following rules, taking analgesic use into consideration (Table 15):
 - If there are at least 14 days of scores for NMPP reported in the eDiary, then the average NMPP score will be used in the assessment of the NMPP responder status. Requiring minimum 14 days of NMPP scores is considered reasonable since this corresponds to at least half of the non-menstrual days from a typical 28-day menstrual cycle.

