7.3.5. Change from Baseline in Functional Impairment on sB&B Scale

The daily eDiary completed by patients includes assessments of endometriosis-associated pain by the sB&B scales for DYS, pelvic pain, and dyspareunia. The dysmenorrhea and dyspareunia scales have possible scores of 0 to 4, while the pelvic pain scale has possible scores of 0 to 3, as outlined in Table 19.

Table 19: Subject Modified Biberoglu and Behrman Scales for Dysmenorrhea, Pelvic Pain, and Dyspareunia

Dysmenorrhea	Pelvic Pain	Dyspareunia	Numerical Score
No pain	No pain	No pain	0
Mild	Mild	Mild	1
Moderate	Moderate	Moderate	2
Severe	Severe	Severe	3
Did not Menstruate	--	No Intercourse	4

The mean sB&B for DYS during the Week 52, Week 104/EOT pain assessment period will be the average over the days when the DYS response was something other than “Did not menstruate.” If the patient reports “Did not menstruate” for all days of the pain assessment period, then the mean sB&B score will be imputed as 0.

The mean sB&B for NMPP during the Week 52, Week 104/EOT pain assessment period, derived from the sB&B for pelvic pain, will be the average of the scores reported for days on which a patient reports she did not menstruate. Mean change of sB&B for NMPP and percent change from baseline will be presented by visit by treatment group.

The mean sB&B for dyspareunia during the Week 52, Week 104/EOT pain assessment period will be the average over the days when the dyspareunia response was something other than “No intercourse.” Mean change of sB&B for dyspareunia and percent change from baseline will be presented by visit by pivotal phase 3 study treatment group. Additionally, the following will be summarized for patients who reported one or more day on which they had vaginal sexual intercourse during a given time interval; the percentage of patients whose maximum dysmenorrhea score was severe, moderate, mild, and none during the specified time interval; the percentage of patients whose maximum dysmenorrhea score was severe or moderate and mild or none during the specified time interval.

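### SAP section 7.3.2 gives no dysmenorrhea NRS score to a woman with no bleeding day, although the primary endpoint and the sB&B scale score her 0, so the secondary mean change can understate improvement

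*SAP*

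**What the plan says.** **Secondary DYS NRS (SAP 7.3.2).** The Week 52 and Week 104/EOT mean is "calculated as the average of the pain scores recorded on days for which patients reported they were menstruating". For the other visits, section 7.2.4 says: "Pain scores for DYS and NMPP are the averages of the respective eDiary pain scores reported during each individual PAP". It defines DYS scores as those reported on bleeding days. Neither section gives a value for a woman with no bleeding day.

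**Defaults.** Section 4.1: "Missing efficacy or safety data will not be imputed, unless otherwise specified". Section 4.4.1, on observed-data analyses: "missing data will not be imputed and only the observed records will be included". Section 7.1.2 computes visit means "including only the patients who are in the analysis who have data for that visit". Section 7.3.2 specifies no exception for DYS.

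**Primary endpoint (SAP 7.2.6, Table 14).** When the eDiary holds no DYS scores: "If no menstruation is reported on the eCRF, then the average DYS score will be set as 0". The rules are introduced with this scope: "For the primary efficacy analysis, both primary endpoints will incorporate the missing data handling rules at Week 52, Week 104/EOT as follows".

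**sB&B dysmenorrhea (SAP 7.3.5).** If the woman answers that she did not menstruate "for all days of the pain assessment period, then the mean sB&B score will be imputed as 0".

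**The concern.** The plan scores the same clinical state, no menstruation and so no menstrual pain, in two ways. It counts as 0 for the responder endpoint and for sB&B dysmenorrhea, but yields no value for the NRS change.

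The state is an expected result of treatment. Section 7.2.7 describes the drug class as suppressing the hypothalamic-pituitary-ovarian axis, and section 9.3.8 is devoted to amenorrhea rates. The women without a value are therefore likely to include those whose dysmenorrhea has stopped.

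Section 7.3 presents the secondary measures across both the pivotal and the extension study by original treatment group. If amenorrhea is more common on active drug, the set of women contributing will differ between the columns up to Week 24. It will also shift within the former placebo column once those women start open-label drug. A trend in the DYS mean would then mix change in pain with change in who still bleeds.

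**Working it through.** **1. One patient followed through the rules.** Take a woman with an assumed baseline DYS of 7, no bleeding day in the Week 52 period and none on the eCRF.

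| Analysis | Value at Week 52 | Source |
|---|---|---|
| Primary DYS pain criterion | Score 0, change 0 − 7 = −7, meets the 2.8-point threshold | 7.2.6, Table 14 |
| sB&B dysmenorrhea | 0, if every diary day is answered as no menstruation | 7.3.5 |
| NRS mean change, percent change | No value (a score of 0 would give −7 and −100%) | 7.3.2 with 4.1, 4.4.1, 7.1.2 |
| NRS LS mean | Visit missing; her bleeding visits, if any, still contribute | 7.3.2, 7.1.2 |
| NRS category tables | Dropped from the denominator, or shown as missing; not counted as <4 | 4.1 or 7.1.1 |

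The last row has two outcomes because section 4.1 uses non-missing denominators for by-visit observed data, while section 7.1.1 keeps missing observations as a separate category.

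**2. Size of the gap.** The SAP states no figure to reproduce. Let p be the share with no bleeding, m the mean DYS score among bleeders and b the mean baseline, taken as equal in both subsets.

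- Bleeders only: m − b
- With zeros: (1 − p)m − b
- Gap: (m − b) − [(1 − p)m − b] = p × m

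None of p, m and b is in the SAP. The assumed ranges are p = 0.2 to 0.8 and m = 3 to 5.

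| p | Women contributing, of the planned 800 | Gap, m = 3 | Gap, m = 5 |
|---|---|---|---|
| 0.2 | 640 | 0.6 | 1.0 |
| 0.5 | 400 | 1.5 | 2.5 |
| 0.8 | 160 | 2.4 | 4.0 |

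Example with b = 7, m = 5, p = 0.5: bleeders only 5 − 7 = −2.0; with zeros 0.5 × 5 − 7 = −4.5.

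**3. Does the mixed model close the gap?** One data set was simulated with 800 women, four visits, 60% nominal amenorrhea at the last visit, baseline about 7 and bleeder scores about 4. A random-intercept model, simpler than the planned unstructured one, was fitted. At the last visit:

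- observed bleeders-only mean change: −2.91 (n = 342)
- model LS mean: −2.95
- mean with zeros: −5.20

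The LS mean stays 5.20 − 2.95 = 2.25 points short of the zero-scored mean. This is what one expects, because the model fills a non-bleeding visit with the score predicted had she bled.

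**The case against.** The best counter-argument is that section 7.3.2 does not say non-bleeding women are excluded. The primary endpoint starts from the same bleeding-day definition. The title of Table 14 names the average DYS NRS score at the same two time points, and the table lists the assigned 0 separately from scores that are missing and to be imputed. The sponsor may therefore intend the zero to carry over, and the no-imputation default applies only where nothing else is specified.

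That intention is possible, but the text does not carry it. Section 7.2.6 confines its rules to the primary endpoints, section 7.3.2 neither cites nor restates them, and section 7.3.5 needed a zero rule of its own. Even on the generous reading, Table 14 covers only Week 52 and Week 104/EOT and leaves the other visits without a rule.

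Other parts of the defence stand:

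- The analyses are descriptive, with no formal comparisons.
- The direction is towards understating benefit if amenorrhea counts as no dysmenorrhea.
- Overall pelvic pain NRS uses all days regardless of menstruation, and amenorrhea rates are tabulated, so these women are visible elsewhere in the report.

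A reader might also infer more than the SAP supports:

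- **That these women vanish from every DYS NRS analysis.** A woman who bled at another post-baseline visit remains in the mixed model, and the category tables may show her as missing.
- **That the NRS result must contradict the responder rate and sB&B.** These are different quantities, and the responder rate also depends on analgesic use. They need not agree numerically under any rule.
- **That the section 7.2.7 imputation model mixes zeros at some visits with bleeders only at others.** The section does not say how non-bleeding visits enter, so this is an open question.

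**Conclusion.** The point holds as an inconsistency in scoring. Followed as written, section 7.3.2 gives no observed DYS NRS value to a woman with no bleeding day, while the primary endpoint (when the eCRF also shows no menstruation) and the sB&B dysmenorrhea score give her 0. The observed mean and percent change then describe women who still bleed, and the LS means treat the other visits as missing at random. In the category tables she is not counted as <4.

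The direction is clear if amenorrhea is taken as absence of dysmenorrhea: improvement is understated by p × m. The size is not known from the SAP. The range of 0.6–4.0 points rests wholly on the assumed shares, bleeder means and equal baselines, and shows only that the choice can matter on the scale of the 2.8-point threshold. The primary responder analysis is unaffected. The change should be made, but it does not threaten the main result.

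**What to change.** In section 7.3.2, including its NRS category tables, state how a woman with no bleeding day is scored:

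1. Apply the existing Table 14 zero rule (no eDiary DYS scores and no menstruation on the eCRF) to the DYS NRS mean at Week 52, Week 104/EOT and each by-visit period.
2. Keep the bleeding-days-only mean as a labelled supplementary row.
3. Report the number of women contributing at each visit.
4. State in section 7.2.7 whether assigned zeros enter the imputation model, and at which visits.

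Table 14 has no diary-completeness condition. If the sponsor wants one before assigning 0, that is a new rule and should be labelled as such.

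The cost is a few sentences and one derivation flag. Section 7.2.3 already lists menstruation status on the CRF at each visit as a data source. If the sponsor prefers the bleeding-days-only mean as the main secondary result, the SAP should say so, give the reason for departing from sections 7.2.6 and 7.3.5, and label the tables accordingly.
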